## **15. STATISTICAL CONSIDERATIONS**

### **15.1. Sample Size and Power Considerations**

Based on efficacy results from study A-101-WART-203 with the same active study medication and treatment plan specified in the current protocol for a comparable patient population and indication, an overall per-wart clearance rate of at least 26% for Active compared with 9% for Vehicle is anticipated. Assuming a distribution of treated warts per subject comparable to the Phase 2 study results, statistical modeling provided a forecast of an advantage in subject responder rates (all treated warts with PWA=0) for Active over Vehicle groups of at least 11 percentage points. This leads to a required sample size for the current study of approximately 500 subjects to provide greater than 90% power to achieve statistical significance in the primary efficacy analysis. This projection takes into account the impact of the anticipated subject dropout rate on power for the primary efficacy analysis, based on the Intent-to-Treat (ITT) population and planned missing data imputation procedures.

Additionally, a simulation was conducted in a manner that accounted for the distribution of multiple warts, the treatment effect in clearance between the different warts and the correlation in wart clearance among multiple warts. Specific details of the simulation are described in the SAP. Results of this simulation indicate that data from 500 subjects (250 per group) will provide 97% power to demonstrate the superiority of 45% A-101 topical solution over vehicle for the primary endpoint.

### **15.2. Analysis of Populations**

The populations used for analyses will be defined as follows:

- Intent-to-Treat Population (ITT): The ITT population includes all randomized subjects.
- Per-Protocol Population (PP): The PP Population includes all subjects who received at least one application of study medication and have no major protocol violations.
- Safety Population: The Safety population includes all subjects who received at least one application of study medication.

### **15.3. Statistical Analysis of Efficacy**

The ITT population will be used for primary and secondary efficacy analyses and summaries. The ITT population is defined as all subjects randomized to the study and analyzed as randomized. The Per-Protocol (PP) population will be used for sensitivity analyses for the primary efficacy analysis and all secondary efficacy analyses included in the hierarchical testing procedure. Details on all analyses discussed below will be provided in the study Statistical Analysis Plan (SAP).

The primary efficacy analysis will be a treatment comparison of A-101 45% compared to Vehicle at Visit 10 (Day 60). It will be based on the proportion of subjects who achieve complete clearance (PWA=0) of all identified common warts. A Cochran Mantel Haenszel

(CMH) test stratified by the baseline number of treated warts will be used to perform the primary efficacy comparison between treatment groups, with 2-tail alpha set at 0.05. The analysis will be based on the ITT population. Any identified common wart for a randomized subject that has missing data at the endpoint visit will be treated as not Clear for the purpose of the primary efficacy analysis.

The first sensitivity analysis for the primary endpoint will be an analysis based upon the PP population. This analysis will use the same CMH model described for the primary analysis. A second sensitivity analysis will be conducted for the primary endpoint using the same CMH model for the ITT population that includes the imputation of missing PWA data using a fully conditionally specified (FCS) regression-based Multiple Imputation (MI) procedure. To assess the impact of missing data imputation on the primary analysis results a tipping point analysis will be conducted. This analysis will shift the treatment coefficient in the regression model used in the MI procedure to impose a worse mean maximum PWA for the A-101 45% arm and a better mean maximum PWA for the vehicle arm. Details of this tipping point analysis will be specified in the SAP. In addition, a model similar to the primary analysis model but stratified instead by Study Center will be performed as a sensitivity analysis including a Breslow-Day test to evaluate heterogeneity across sites.

Four secondary efficacy analyses will be performed and tested in a hierarchical Fixed-Sequence step-down method to control alpha among secondary efficacy variables. The predefined order of the tests is specified to be the order of these analyses as presented below. All analyses will be conducted at the same alpha level (2-tail alpha = 0.05). The results of the second analysis will only be reported if the first analysis reaches statistical significance at alpha = 0.05. The results of the third analysis will only be reported if the first and second analyses reach statistical significance, each at alpha = 0.05. The results of the fourth analysis will only be reported if the first, second and third analyses reach statistical significance, each at alpha = 0.05. Each of the analyses will focus on the outcome of identified common warts at specified time points.

The first secondary analysis will evaluate the effectiveness of A-101 45% compared to Vehicle at Visit 13 (Day 137). It will be based on the proportion of subjects who achieve complete clearance (PWA=0) of all identified common warts. A Cochran Mantel Haenszel (CMH) test identical to the primary efficacy analysis model and stratified by the number of treated warts at baseline will be used to perform the comparison between treatment groups, with 2-tail alpha set at 0.05. Any randomized subject with missing data at the Day 137 visit will be treated as not Clear for the purpose of this secondary efficacy analysis. Sensitivity analyses specified for the primary efficacy analysis will also be performed for this efficacy time point, including missing data imputation impact analyses, the tipping point analysis, and the site heterogeneity analysis.

The second secondary efficacy analysis will be based on a comparison between A-101 45% and Vehicle of the mean per-subject percent of treated warts that are Clear (PWA=0) at Visit 13 (Day 137), using an analysis of variance (ANOVA) model with 2-tail alpha set at 0.05.

The third secondary efficacy analysis will be a comparison between A-101 45% and Vehicle of the proportion of subjects with a single wart at baseline, whose wart is Clear (PWA=0) at Visit 10, using a CMH test stratified by investigator site, with 2-tail alpha set at 0.05.

The fourth secondary efficacy analysis will a comparison between A-101 45% and Vehicle s with respect to the median time to achieve onset of Clearance (PWA=0) for all treated warts. It will be conducted as a comparison of median time for a subject to first achieve Clearance (PWA=0) of all treated warts, using a log rank test with 2-tail alpha set at 0.05. This will be a Kaplan-Meier time-to-event analysis providing standard survivor functions and comparisons of time-to-event curves using the log rank test, where time-to-event curves will be compared with two-tail alpha = 0.05, and median time to event will be presented for each treatment group. For each subject the time to achieve onset of complete treated wart Clearance will be calculated from the date of randomization to the earliest visit date when all treated warts are clear. In the event a subject does not attain complete wart Clearance, that subject's time-to-event data will be treated as censored for the Kaplan-Meier analysis.

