**Study Endpoints:**

*Primary Efficacy Endpoint:*

The primary efficacy endpoint is the proportion of subjects whose identified common warts are determined to be clear on the PWA scale (PWA=0) at Visit 10 (Day 60).

*Secondary Efficacy Endpoint:*

The secondary efficacy endpoints are:

- Proportion of subjects whose identified common warts are clear on the PWA scale (PWA =0) at Visit 13 (Day 137; last follow-up evaluation).
- Mean per-subject percent of all warts that are clear on the PWA scale at Visit 13 (Day 137)
- Proportion of subjects with a single wart at baseline whose wart is clear on the PWA scale (PWA=0) at Visit 10 (Day 60)
- Median time for subjects to achieve clearance (PWA=0) of all treated common warts.

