#### **6.1.2. Secondary Objectives**

The secondary objectives of this study include:

- Duration of response to A-101 45% compared to Vehicle.
- Onset of action of A-101 45% compared to Vehicle.
- Safety of A-101 45%.

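### Section 15.3 makes the reporting of three secondary results, not only the claim of significance, depend on earlier p-values, with no gain in alpha control

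*Protocol*

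**What the plan says.** Section 15.3 of the protocol says the four secondary analyses are to be performed and are "tested in a hierarchical Fixed-Sequence step-down method to control alpha among secondary efficacy variables". The order is fixed and each test uses two-sided alpha of 0.05:

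1. Subject-level complete clearance at Day 137.
2. Mean per-subject percent of treated warts clear at Day 137.
3. Clearance at Visit 10 among subjects with a single wart at baseline.
4. Time to clearance of all treated warts.

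Three sentences then set the conditions:

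- Second: "The results of the second analysis will only be reported if the first analysis reaches statistical significance at alpha = 0.05".
- Third: "The results of the third analysis will only be reported if the first and second analyses reach statistical significance".
- Fourth: "The results of the fourth analysis will only be reported if the first, second and third analyses reach statistical significance".

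Other text in Section 15.3 carries no such condition. It states that "The ITT population will be used for primary and secondary efficacy analyses and summaries", plans per-protocol sensitivity analyses of every secondary in the hierarchy, and says of the fourth analysis that "median time to event will be presented for each treatment group".

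The fourth endpoint appears in the synopsis list as "Median time for subjects to achieve clearance (PWA=0) of all treated common warts". Section 6.1.2 gives as one of the secondary objectives "Onset of action of A-101 45% compared to Vehicle".

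**The concern.** Under a fixed sequence, once one test misses 0.05, no later hypothesis may be claimed. That restriction is all that error control needs. Section 15.3 goes further and restricts the reporting of the later results. Followed as written, whether a prespecified endpoint appears in the report would depend on the p-value of a different endpoint.

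The effect is clearest for time to clearance. It stands last in the order and is the only listed endpoint that speaks to onset of action. If an earlier secondary missed 0.05, a stated secondary objective could be left without any reported result, and nothing would be gained in type I error.

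**Working it through.** **1. The plan's error rate, and whether the reporting condition contributes to it.** The inputs from Section 15.3 are four ordered tests at two-sided 0.05. Let k be the position of the first true null hypothesis in the order. Any false claim requires that this hypothesis be rejected, so

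P(any false claim) ≤ P(|Z_k| > 1.96) = 0.05,

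with equality when k = 1. This reproduces the intended control at 0.05. The argument uses only the order and the p-values; the printing of later results appears nowhere in it. The bound is therefore the same under the protocol's rule and under a rule that reports everything but gates the claims.

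A simulation agrees, as it must by construction. It used 1,000,000 runs with four normal test statistics; the correlations and the 90% power are assumptions, not protocol figures.

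| Scenario | Correlation 0 | 0.5 | 0.8 |
|---|---|---|---|
| All four nulls true, claims gated | 0.0503 | 0.0499 | 0.0501 |
| First 1 to 3 effects real (90% power each), rest null | 0.036 to 0.045 | 0.031 to 0.039 | 0.026 to 0.030 |

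The claims were identical in every simulated trial under both rules. For contrast, four independent tests with no gate on claims would give 1 − 0.95^4 = 0.185. The claim gate does the work, and it should stay.

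**2. What is lost under the literal reading.** If the sequence first fails at step j, the results after step j are withheld, which is 4 − j of the four:

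- Failure at step 1 (for example p = 0.051): 4 − 1 = 3 withheld.
- Failure at step 2: 4 − 2 = 2 withheld.
- Failure at step 3: 4 − 3 = 1 withheld, namely time to clearance.

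How often this would happen cannot be derived, because the protocol gives no power for any secondary analysis.

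**3. Which objective is exposed.** The first three secondaries are clearance measures at one fixed visit (Day 137 or Visit 10). Only the fourth measures when clearance occurs. The step just before it uses only subjects with a single baseline wart, in a CMH test stratified by site. With about 500 subjects at about 25 centers, a site averages 500 / 25 = 20 subjects before that restriction. The size of the subset is not stated, so no probability of a miss is offered.

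**4. Whether the text supports the literal reading.** The hierarchy paragraph first says that all four analyses are carried out and tested, and then conditions what is reported. It thus separates doing an analysis from reporting it, which favours the literal reading. The sentence on presenting median time to event by arm carries no condition, which points the other way. It is unclear beside the gating sentences, but it is not a firm contradiction, since it could be read as describing the analysis once the gate is open. No sentence in the protocol says that results after a failed step are shown descriptively.

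**The case against.** The strongest reply is that the wording is shorthand. The sentences sit in a paragraph whose declared purpose is alpha control, so reporting may mean reporting as confirmatory. Three other statements fit that view: all four analyses are performed without condition, per-protocol sensitivity analyses are planned for every secondary in the hierarchy, and the medians for the fourth are to be presented by arm. Sensitivity analyses of results that are never shown would serve little purpose. How results after a failed step are displayed is also commonly settled in the SAP, which was not available for this review. Finally, the calculation shows only that the reporting condition is neutral for type I error. It does not measure harm.

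Much of this stands. The narrower reading is plausible, and no probability of withholding can be given. But this is not a gap left to the SAP: the protocol states a rule, states it three times, and applies it to results rather than to claims. A reader who follows it would withhold those results. If the narrower meaning was intended, the correction merely makes the text say so.

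**Conclusion.** The point holds. As written, Section 15.3 ties the reporting of three of the four secondary results to earlier p-values, and this contributes nothing to error control. The fixed sequence bounds family-wise error among the secondaries at 5% with or without it.

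The importance is minor to moderate. The primary endpoint, the first secondary, alpha control and the sample size are untouched. After a failed step the later endpoints could not be claimed as confirmatory under corrected wording either, so what is at stake is their descriptive reporting, including the only listed evidence on onset of action. The conclusion about withheld results rests on the literal reading and on at least one of the first three secondary tests missing 0.05.

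**What to change.** In the three gating sentences of Section 15.3, replace the condition on reporting with a condition on the claim: the second, third and fourth analyses *will be declared statistically significant only if* all preceding secondary analyses are significant at two-sided 0.05.

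Then add one sentence: *The results of all four secondary analyses are reported regardless; those after the first non-significant step are labelled descriptive, with effect measures and intervals as set in the SAP.* This also settles how the sentence on presenting median time to event is to be read.

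The cost is three reworded sentences and one new one. All four analyses are already planned, and the test order, alpha and sample size do not change. The one small drawback is that non-confirmatory results will appear in the report and must be clearly labelled as such.

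### The fourth secondary endpoint is named and described as a comparison of median times to clearance, but the vehicle median will almost certainly not be reached, and timing by actual visit date can print a spurious median

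*Protocol*

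**What the plan says.** The synopsis (Study Endpoints) lists the fourth secondary endpoint as "Median time for subjects to achieve clearance (PWA=0) of all treated common warts".

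Section 15.3 uses the median three times in one paragraph:

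- The arms are compared "with respect to the median time to achieve onset of Clearance (PWA=0) for all treated warts".
- The method is then stated: "It will be conducted as a comparison of median time for a subject to first achieve Clearance (PWA=0) of all treated warts", with a two-sided log-rank test at 0.05.
- Lastly, "median time to event will be presented for each treatment group".

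Between the second and third of these, the same paragraph describes a Kaplan-Meier analysis "providing standard survivor functions and comparisons of time-to-event curves using the log rank test". That is the correct account of the test.

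Each subject's time is "calculated from the date of randomization to the earliest visit date when all treated warts are clear". Subjects who never clear are censored. The last assessment is Visit 13, Day 137, with a window of +7 days (Table 2), so it can fall as late as Day 144.

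The planning rates are in Section 15.1: "an overall per-wart clearance rate of at least 26% for Active compared with 9% for Vehicle is anticipated", and "an advantage in subject responder rates (all treated warts with PWA=0) for Active over Vehicle groups of at least 11 percentage points". Neither subject-level rates by arm nor the day to which the rates refer are given.

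**The concern.** One paragraph gives the log-rank test two targets, medians and curves, and only the second is right. The endpoint's name also promises a result, a shorter median time on active than on vehicle, that needs at least 50% complete clearance in both arms. The planned rates are far below that on vehicle. A significant log-rank result would then have no matching comparison of medians, although onset of action against vehicle is a stated secondary objective (Section 6.1.2).

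The date rule raises a second, separate problem. Subjects who have not cleared are censored at their own Visit 13 date, and those dates spread over Days 137 to 144. Events in that week are divided by an ever smaller risk set. The curve can fall below 50% there although fewer than half of the subjects have cleared, and the table would then show a median that is an artefact.

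**Working it through.** **1. The plan's own figure.** Inputs from Section 15.1: 250 per arm, two-sided alpha 0.05, gain of 11 points, power above 90% (97% by simulation). Two-proportion formula:

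z = [d − 1.96·√(2·p̄(1−p̄)/n)] / √{[p1(1−p1) + p2(1−p2)]/n}

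For 20% against 9%: d = 0.11, p̄ = 0.145, z = (0.11 − 1.96 × 0.03149)/0.03111 = 1.55, power 94.0%. At vehicle rates of 5%, 6% and 12% the power is 98.2%, 97.3% and 90.2%. So the stated power is reproduced with vehicle responder rates of about 12% or less, far from 50%. This supports a low vehicle rate. It does not bound the active rate, because 11 points is a minimum.

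**2. Can the medians be reached by Day 137?** Assumptions: the Section 15.1 rates are Day 60 rates, and they serve as upper values for the all-warts-clear rate (true if per-wart clearance does not depend on how many warts a subject has). First clearance at any visit counts, so the Day 60 pace is carried on to the end at constant hazard:

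cumulative clearance = 1 − (1 − p)^(137/60)

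| Day 60 rate p | By Day 137 |
|---|---|
| Vehicle 9% | 1 − 0.91^2.283 = 19.4% |
| Vehicle 12% | 25.3% |
| Active 20% (9% + 11 points) | 39.9% |
| Active 23% | 44.9% |
| Active 26% | 49.7% |

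To reach 50% by Day 137 an arm needs p = 1 − 0.5^(60/137) = 26.2% at Day 60, which is 26.2/9 = 2.9 times the planned vehicle rate. At 9% the extrapolated vehicle median is 60 × ln 0.5 / ln 0.91 = Day 441.

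Simulation with 250 per arm, the Table 2 visit windows, continued clearing and 12% dropout (assumed), on nominal days: at vehicle rates of 9 to 12% the curve reached 50% in 0 of 2,000 runs. At active 20% it did so in under 1% of runs, and at active 26% in about half.

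**3. What timing by actual visit date does.** Take active at 20% by Day 60 with continued clearing.

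- Not yet clear at Visit 12 (Day 106): 0.80^(106/60) = 0.674.
- Share of these clearing between Visits 12 and 13: q = 1 − 0.80^(31/60) = 0.109.
- Nominal days: one step at Day 137, 0.674 × (1 − 0.109) = 0.601, so 40% clear, as is true.
- Actual dates, attendance spread evenly over the 8 days 137 to 144 (assumed) and the extra days of clearing ignored: with k eighths of the subjects still to be seen, each day multiplies the curve by (1 − q/k). The product over k = 8, 7, …, 1 is 0.737. Then 0.674 × 0.737 = 0.497, so the curve shows 50.3% clear.

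No subject behaves differently in the two versions. The 10 points come only from dividing by those not yet seen. Simulation, which also includes dropout and clearing up to Day 144, gives an average of about 53 to 59% for the same true 40%, the higher values when attendance is concentrated near Day 137. A median is printed in about 68 to 76% of runs.

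The same arithmetic for vehicle at 9% (q = 0.048, 0.91^(106/60) = 0.847, product 0.877) gives 0.847 × 0.877 = 0.743, or 25.7% shown against 19.4% true. A vehicle median was printed in 0 to about 12% of simulated runs, depending on attendance. These fell late in the Visit 13 window and rested on few subjects.

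**The case against.** **The paragraph largely corrects itself.** An analyst who reads on finds the log-rank test described as a comparison of curves, with origin, event and censoring defined, and would run the right test. This stands. A reader might infer that the test is invalid or that the error rate is at risk. The documents do not support that: the log-rank test needs no median, and the fixed sequence is unaffected. This is also the last of four gated secondary tests.

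**A median that is not reached is ordinary Kaplan-Meier output, and such conventions belong in the SAP.** This stands for a descriptive line and for anything the protocol merely leaves open. It does not cover what the protocol states: the median is the endpoint's name, and the test is said to compare medians.

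**The rates are assumed.** The day of the 26% and 9% rates and the subject-level rates are not given, and independence of clearance from wart count may fail. For vehicle this matters little. Every fully cleared subject contributes at least one cleared wart, so the subject rate cannot exceed 9% times the mean number of warts. Reaching 26.2% would need a mean of about 2.9 and every cleared wart on a single-wart subject.

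For active it matters a great deal. A reader might infer that the active median cannot be reached either. That is not supported: 26% and 11 points are minimum values, and 26% carried forward lands almost exactly at 50%. Under the protocol's own date rule with continued clearing, an active median would usually be printed (more than 90% of runs at 23% or 26%), though mostly as a tail artefact.

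**The window problem is a separate issue, and its size is assumed.** Both true. If 80% of clearances come by Visit 10, the inflation is small: a true 23% shows as 25.8 to 27.3%. The mechanism, however, follows from the date rule and the +7-day window that the protocol fixes.

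**Conclusion.** The point holds as a minor correction.

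- The endpoint's name and the description of the log-rank test as a comparison of medians are wrong as written. This needs no assumption.
- The vehicle median will almost certainly not be reached: about 19% cumulative clearance by Day 137 from 9% at Day 60, and 25% from 12%, against the 50% needed. This assumes that the planning rates are Day 60 rates usable at subject level and that clearing goes on at the same pace.
- Whether the active median is reached is uncertain.
- Timing by actual visit date can inflate the end of the curve, by about 10 to 19 points when the true value is 40% and clearing continues. The size depends on assumed attendance and dropout and is much smaller if clearing is mostly done by Visit 10.

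The choice of the log-rank test, type I error, the testing order and the other endpoints are not affected.

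**What to change.** In the synopsis and Section 15.3:

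1. Rename the endpoint *time to first complete clearance (PWA=0) of all treated warts*.
2. Describe the log-rank test only as a comparison of the time-to-clearance curves.
3. Use nominal visit days for both the curves and the test, so that the two rest on the same times and the Visit 13 window does not distort the tail.
4. Report Kaplan-Meier cumulative clearance per arm with 95% CI at Visit 10 and Visit 13, and the median only if it is reached.

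A hazard ratio with 95% CI may be added. It is optional, since it brings a proportional-hazards assumption that the log-rank test does not need.

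The cost is one endpoint line and one paragraph reworded, trivial programming, and a small change in the time variable fed to the log-rank test. No new data are needed, and alpha control and the testing order do not change.

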### **8.3. Removal of Subjects from Study Therapy**

A subject may be removed from the study therapy for a variety of reasons, including:

- Unacceptable adverse event
- Subject unwilling or refusal to continue with the protocol defined study visits and/or consent withdrawal for study participation
- Change in compliance with an inclusion/exclusion criteria
- Use of a prohibited medication (through Visit 13)
- General or specific changes in the subject's condition that render the subject unacceptable for further treatment in this study in the judgement of the investigator.

Aclaris Therapeutics, Inc.

Protocol Number: A-101-WART-301

Amendment 3: Version 5 14 February 2019

If a subject is to be withdrawn from the study, the Aclaris Therapeutics, Inc. CRA or designee must be informed within 24 hours of the decision to remove the subject from the study.

The study may be discontinued at the discretion of Aclaris Therapeutics, Inc. Some examples of reasons for discontinuation are the occurrence of the following:

- Increased frequency, severity or duration of known AEs
- Medical, regulatory or ethical reasons affecting the continued performance of the study
- Difficulties in the recruitment of subjects

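### The log-rank test of time to all-warts clearance leaves out the baseline wart-count strata used in the primary and first secondary tests, and so gives up a little precision

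*Protocol*

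**What the plan says.** All of this is in Protocol Section 15.3.

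- **Fourth secondary.** The outcome is time to clearance of all treated warts, "calculated from the date of randomization to the earliest visit date when all treated warts are clear". The arms are compared "using a log rank test with 2-tail alpha set at 0.05". No stratification factor is named. For a subject who does not clear, "time-to-event data will be treated as censored for the Kaplan-Meier analysis"; no censoring date is given.
- **Primary and first secondary.** Both test the proportion of subjects with all identified warts clear, at Visit 10 and Visit 13. Both use a CMH test stratified by baseline number of treated warts. Missing data count as not Clear: for the primary, a wart that "has missing data at the endpoint visit will be treated as not Clear"; for the first secondary, "Any randomized subject with missing data at the Day 137 visit will be treated as not Clear".
- **Second and third secondaries.** The second is an ANOVA of the per-subject percent of warts clear, with no strata named. The third is restricted to subjects with a single baseline wart and is stratified by site.
- **Testing order.** The fourth analysis is last in a fixed sequence: "The results of the fourth analysis will only be reported if the first, second and third analyses reach statistical significance".

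Section 15.3 leaves details of the analyses to the SAP.

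**The concern.** Three tests in the plan address the same subject-level outcome, all warts clear, in the whole randomized population. Two adjust for how many warts the subject started with. The third, time to that outcome, does not. A subject with six warts must clear all six to count as an event, while a subject with one must clear only one. Wart count therefore bears on time to clearance just as it bears on clearance at a fixed visit. An unstratified comparison mixes subjects with very different chances of an event, and the treatment contrast becomes slightly less sharp.

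What is at stake is a modest amount of precision in a confirmatory test. Its validity is not in question.

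**Working it through.** **Inputs.** From Protocol Section 15.1: per-wart clearance of 26% (active) and 9% (vehicle), 250 subjects per group, a responder difference of at least 11 points, and 97% power for the primary. Not given, so assumed:
- Share of subjects with 1 to 6 warts: 45/20/12/10/7/6% (mix A) or 30/20/15/15/10/10% (mix B).
- Within-subject correlation ρ of wart clearance: 0 to 0.6.
- Dropout: 5% to 20%, with 10% as the base case.
- Clearance times spread over the scheduled visits.

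**Step 1: the plan's own figure.** The protocol gives no power for the time-to-clearance test, so the check is on the primary. Power = Φ{[d − 1.96·√(2p̄(1−p̄)/n)] / √[(p₁(1−p₁)+p₂(1−p₂))/n]}. The vehicle responder rate is not stated. With 17% against 6%, d = 0.11, p̄ = 0.115 and n = 250:
- 1.96·√(2 × 0.115 × 0.885/250) = 0.0559
- √[(0.1411 + 0.0564)/250] = 0.0281
- Φ[(0.11 − 0.0559)/0.0281] = Φ(1.92) = 97.3%

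Vehicle rates of 4% to 8% give 98.9% to 95.2%. Built up from warts with mix A, ρ = 0.2 gives 15.0% against 4.7% (power 97.2%) and ρ = 0.4 gives 17.2% against 5.5% (98.7%). The stated 97% is reproducible, so these scenarios fit the plan.

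**Step 2: how strongly wart count predicts the outcome.** With a beta-binomial model, P(all k clear) is the product over j = 0 to k−1 of [p(1−ρ)+jρ]/[(1−ρ)+jρ]. On active (p = 0.26):
- One wart: 26%.
- Six warts, ρ = 0: 0.26⁶ = 0.03%.
- Six warts, ρ = 0.4: 0.26 × 0.556 × 0.683 × 0.753 × 0.798 × 0.829 = 4.9%.

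Even with substantial correlation, the chance of an event falls more than fivefold from one wart to six.

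**Step 3: gain from stratifying.** Simulated trials had 250 subjects per arm and 10% dropout in each arm. Leavers were subjects who would not have cleared, censored at their last visit. Each setting had 300 runs. Efficiency ratio = (stratified mean z / plain mean z)².

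| Setting | Plain z | Stratified z | Efficiency ratio |
|---|---|---|---|
| Mix A, ρ = 0.4 | 4.14 | 4.23 | 1.044 |
| Mix B, ρ = 0.2 | 3.39 | 3.48 | 1.054 |
| Mix A, ρ = 0 | 3.56 | 3.70 | 1.080 |

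Separate simulations used 12% random dropout, 30% to 60% single-wart subjects and a subject random-effect SD of 0.7 to 2.5. They gave ratios of 1.02 to 1.07. All simulations at these per-wart rates together span about 1% to 9%, with the largest gain at low correlation. In subjects: 500 × 0.01 = 5 to 500 × 0.09 = 45.

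**Step 4: power.** In the three table rows, simulated power was 99.0% and 99.0%, 96.7% and 96.7%, and 96.0% and 97.0% (plain, then stratified). By the normal approximation the last row gives Φ(3.56 − 1.96) = 94.5% against Φ(3.70 − 1.96) = 95.9%, a gain of 1.4 points. About 2 points is the upper end.

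**Step 5: validity.** With no treatment effect and 10% dropout in each arm (1,500 runs), both tests rejected in 4.7% of trials. A separate null simulation gave 5.3% and 5.5% for the two tests. The Monte Carlo SE with 1,500 runs is √(0.05 × 0.95/1500) = 0.6 points, so neither test shows inflation.

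**The case against.** **Against the strata.** An unstratified log-rank test is valid, and randomization is stratified by site (Section 10.2), so the design does not oblige anyone to use wart count. The gain is small. Both statements stand. It can also be said that the second and third secondaries do not use wart count. That carries little weight: the second analyses a percentage of warts, and the third contains only single-wart subjects, for whom the factor is constant. Finally, the SAP may add the strata. If it does, the point is met. But Section 15.3 names strata wherever it uses them in the CMH tests, so its silence here reads as unstratified.

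**A stronger reading that the documents do not support.** A reader might infer that censoring non-clearers conflicts with the not-Clear rules, overstates clearance over time and raises the error rate.
- The protocol gives no censoring date. Censoring at Day 137 is as compatible with its text as censoring at the last visit, and the SAP may settle it.
- The not-Clear rules are each confined to their own fixed-visit analysis. The primary's reads "missing data at the endpoint visit will be treated as not Clear for the purpose of the primary efficacy analysis". Censoring subjects without the event is the usual convention.
- The effect on the test depends mainly on unequal, informative leaving, for which the protocol gives no figures. With 10% never-clear leavers in each arm, mean z is 4.14 (last visit) against 4.12 (Day 137). With 20% active and 5% vehicle leaving it is 4.53 against 4.11, and with 5% and 20% it is 3.74 against 4.09.
- Null rejection of 6.2%, seen with 20% active and 5% vehicle never-clear leavers, is for the test taken alone. The fixed sequence reaches it only after three significant results. With no effect at all, the first of these already holds that chance to about 5%.
- Carrying leavers to Day 137 is itself a trade-off. If 10% leave at random, last-visit censoring estimates active clearance at 17.4% against a true 17.3%, while the not-Clear rule gives 16.4%.

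**Conclusion.** The point holds as a minor loss of precision. As written, the fourth secondary is the only whole-population test of all-warts clearance that leaves out baseline wart count. The size rests on the plan's per-wart rates together with the assumed wart mixes, correlations, clearance timing and dropout. Higher within-subject correlation shrinks the gain. The protocol's text does not show an error in the main censoring rule or an inflated error rate for the sequence, and neither is claimed here.

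**What to change.** In Section 15.3, or in the SAP before unblinding, state that the log-rank test for the fourth secondary is stratified by baseline number of treated warts, with the same categories as the primary CMH test. The Kaplan-Meier curves can stay unstratified as description. This costs one phrase and no new data, since wart count is already collected and used in the primary. There is no material downside: strata with no events simply contribute nothing.

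Optionally, and only as a sensitivity analysis, repeat the test with early leavers who never cleared carried as not Clear to Day 137, to match the missing-data rule of the primary and first secondary. This costs one extra run. It should be read as conservative about the level of clearance, because it understates clearance if leaving is unrelated to response.
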